### 3. Assisted shoulder forward elevation

Reproduced with permission from *OrthoInfo*. © American Academy of Orthopaedic Surgeons. <http://orthoinfo.aaos.org>.

This exercise can be done either lying down (A) or sitting down (B).

Clasp hands together and lift arms above head.

Keep your elbows as straight as possible.

Maintain the elevation for 10-20 seconds, then slowly lower your arms.

Slowly increase the elevation of your arms as the days progress, using pain as your guide.

Repeat 10 times per session, do 2 sessions a day.

### 4. Lateral finger walk

Reproduced with permission from *OrthoInfo*. © American Academy of Orthopaedic Surgeons. <http://orthoinfo.aaos.org>.

Stand with your side toward a wall three-quarters of an arm's length away from the affected arm.

Reach out and touch the wall at waist level with the fingertips of the affected arm.

With your elbow slightly bent, slowly walk your fingers up the wall, spider-like, until you've raised your arm as far as you comfortably can. Your fingers should be doing the work, not your shoulder muscles.

Slowly lower the arm (with the help of the good arm, if necessary) and repeat.

Perform this exercise 10 times per session, do 2 sessions a day.

## 5. Outward rotation and inward rotation

Reproduced with permission from *OrthoInfo*. © American Academy of Orthopaedic Surgeons. <http://orthoinfo.aaos.org>.

Keep your elbow at side of your body or place your elbow on top of a table with proper height.

Slide forearm back and forth, as shown to the maximum degree without pain.

Repeat 10 times per session, do 2 sessions a day.

## 6. Towel stretch

Image courtesy of [HealthyAndNaturalWorld.Com](http://HealthyAndNaturalWorld.Com)

Hold one end of a towel behind your back and grab the opposite end with your other hand.

Hold the towel in a horizontal position. Use your good arm to pull the affected arm upward to stretch it.

Do this 10 times per session, do 2 sessions a day.

## APPENDIX D: INSTRUCTIONS FOR MEASURING RANGE OF MOTION OF THE GLENOHUMERAL JOINT WITH A GONIOMETER^1

**Instrument:** Goniometer (Medigauge® electronic digital goniometer for orthopedics, chiropractic, sports medicine, animal science, occupational therapy, physical therapy, and research)

**Patient position:** Sitting or supine position

**Scapular position:** Stabilize the scapula by grasping the coracoid process and the spine of the scapula posteriorly (2 people may be needed to fully inhibit scapular motion).

### Glenohumeral joint flexion

To measure flexion range of motion (ROM), the patient must be in sitting or supine position with the arm comfortably by the side.

- The patient will be asked to actively flex the shoulder with his/her palm facing medially to end range in the sagittal plane (with no compensatory movements from the thorax or the lumbar spine). Range of motion will be measured by placing the axis of the goniometer over the humeral head. The stationary arm will be aligned with the midline of the trunk. The movable arm will be aligned with the lateral epicondyle.
- For passive ROM, the examiner will passively flex the shoulder with the patient's palm facing medially until end range is reached and measures as above.

---

1. Magee D. Orthopedic Physical Assessment. 6th edition. Saunders. 2013

### Glenohumeral joint abduction

To measure abduction ROM, the patient must be in a sitting or supine position with the arm comfortably by his/her side.

- The patient will be asked to actively abduct the shoulder in external rotation position (palm facing up) to end range (shoulder must remain in the frontal plane). Range of motion will be measured by placing the axis of the goniometer over the anterior aspect of the acromion process.. The stationary arm will be aligned parallel with the midline of the sternum. The movable arm will be aligned with the midshaft of the humerus.
- For passive ROM, the examiner will passively abduct the shoulder with the patient's palm facing up until end range is reached and measures as above.

### Glenohumeral external rotation

To measure external rotation ROM with the shoulder in the adduction position, the patient must be in a sitting or supine position. Place a folded towel under the humerus to keep the shoulder and elbow level with the elbow flexed to 90° (palm facing medially) and the forearm perpendicular to the floor.

- The patient will be asked to actively externally rotate the shoulder to end range. Range of motion will be measured by placing the axis of the goniometer on the olecranon process. The stationary arm will be perpendicular to the floor. The movable arm will be aligned with the ulnar styloid process.
- For passive ROM, the examiner will passively externally rotate the glenohumeral joint until end range is reached and measures as above.

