## 4 SELECTION AND WITHDRAWAL OF PATIENTS

### 4.1 Inclusion Criteria

A patient who meets all of the following criteria will be eligible to participate in the study:

1. Has 1 of the following diagnoses (can be diagnosed at the Screening Visit) and meets the following criteria:
  - a. Glenohumeral OA:
    - Male or female, 35 to 80 years of age, inclusive, on the day of consent.
    - Painful symptoms associated with OA of the index glenohumeral joint for  $\geq 3$  months prior to the Screening Visit.
    - Grade 2 or 3 OA in the index glenohumeral joint based on the Samilson-Prieto classification system as confirmed by X-ray (axillary view and true anterior-posterior view) taken at the Screening Visit or within 6 weeks of the Screening Visit.
  - b. Shoulder AC:
    - Male or female, 35 to 80 years of age, inclusive, on the day of consent.
    - Pain associated with AC of the index joint for  $\geq 1$  month but  $\leq 6$  months prior to the Screening Visit.
    - More than 20% (25% if dominant shoulder is the index shoulder) loss of passive range of the rotation arc (external and internal rotation) of glenohumeral movement, measured with the patient in supine or sitting position and the shoulder elevated to 45 degrees, compared with the contralateral shoulder.
    - No X-ray evidence of OA of the index shoulder (axillary view and true anterior-posterior view) at the Screening Visit or within 6 weeks of the Screening Visit.
2. Is willing and able to sign the informed consent form (ICF), indicating that the patient understands the purpose of the study and procedures required for the study before the initiation of any study-specific procedures. Patients who are unable to provide informed consent will not be included in the study.
3. Is willing and able to comply with the study procedures and visit schedules and able to follow verbal and written instructions.
4. Has a body mass index (BMI)  $\leq 40$  kg/m^2.
5. Has an average daily mean shoulder pain with movement score  $\geq 5.0$  and  $\leq 9.0$  in the index shoulder (0 to 10 NRS) using the average daily ratings for at least 5 out of the 7 days prior to Day 1.

Note: The required mean average daily shoulder pain with movement score will not be disclosed to the patient.
6. Has shoulder pain present  $> 15$  days in the month prior to the Screening Visit.

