### **6.3 Screening Visit (Days -21 to -1)**

The study will include a Screening Period of a maximum of 21 days. The following procedures will be performed at the Screening Visit:

- Obtain informed consent.
- Confirm eligibility based on Inclusion and Exclusion Criteria (see Sections 4.1 and 4.2, respectively).
- Complete APR and PRR trainings prior to patient questionnaires.
- Administer the PD-Q, PHQ-9, GAD-7, PCS, and ISI.
- Record medical history, including OA medical history and AC medical history.
  - For glenohumeral OA patients, OA medical history will include American College of Rheumatology diagnosis details; OA diagnosis date (if available); number of days with index shoulder pain in the last month; previous IA corticosteroid, PRP, or hyaluronic injections; presence of OA in other joints; and prior procedures or surgeries for index shoulder OA.
  - For AC patients, AC diagnosis date (if available); pain duration since onset at Screening; previous IA corticosteroid, PRP, or hyaluronic injections; presence of OA in other joints; and prior procedures or surgeries for index shoulder AC.
- Record patient demographics.
- Record prior treatments and medications.
- Record the average daily shoulder pain with movement score (0 to 10 NRS), SI question, and rescue medication usage in the eDiary.
- Record the pain with duration since onset (AC patients only).
- Perform physical examination.
- Perform shoulder assessment, including active and passive ROM, on the index and contralateral shoulder.

- Perform index shoulder X-ray.
  - X-ray of the index shoulder will include axillary view and true anterior-posterior view.
  - For glenohumeral OA patients, the Screening Visit X-ray will be read centrally to confirm Grade 2 or 3 OA in the index glenohumeral joint based on the Samilson-Prieto classification system.
  - For shoulder AC patients, the Screening Visit X-ray will be read centrally to confirm there is no evidence of OA in the index shoulder.
  - An x-ray acquired within 6 weeks of the Screening Visit may be used for study qualification if the specified imaging protocol was followed. The x-ray will be read centrally to confirm there is no evidence of OA in the index shoulder.
- Obtain vital signs.
- Perform ECG.
- Record height and weight and calculate BMI.
- Collect blood samples for hematology and chemistry, including hemoglobin A1c.
- Perform HIV, HBsAg, and HCV screens.

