### Glenohumeral internal rotation in 45° or comfortable abduction

Internal rotation ROM must be measured with the patient in a sitting or supine position, the shoulder abducted to 45° or comfortable position, and the elbow flexed to 90°. Place a folded towel under the humerus to keep the shoulder and elbow level.

- The patient will be asked to actively internally rotate the shoulder with his/her palm facing medially to end range without scapular compensation. Range of motion will be measured by placing the axis of the goniometer on the olecranon process. The stationary arm will be perpendicular to the floor. The movable arm will be aligned with the ulnar styloid process.
- For passive ROM, the examiner will passively internally rotate the glenohumeral joint until end range is reached, ensuring that there is no scapular compensation.

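### Appendix D permits sitting for external rotation, but its set-up and vertical goniometer reference work only supine, and no section holds a patient's posture constant across visits

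*Combined protocol and SAP*

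**What the plan says.** Protocol Appendix D opens by giving the patient position for all range of motion (ROM) readings as "Sitting or supine position", and repeats the choice for each movement.

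- **External rotation.** "To measure external rotation ROM with the shoulder in the adduction position, the patient must be in a sitting or supine position". A towel under the humerus brings shoulder and elbow to one height, "with the elbow flexed to 90° (palm facing medially) and the forearm perpendicular to the floor". For the goniometer: "The stationary arm will be perpendicular to the floor".
- **Internal rotation.** "Internal rotation ROM must be measured with the patient in a sitting or supine position, the shoulder abducted to 45° or comfortable position". It adds: "Place a folded towel under the humerus to keep the shoulder and elbow level". The stationary arm is again vertical.
- **Flexion and abduction.** The stationary arm follows the trunk midline or the sternum, so these readings do not depend on posture in this way.

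Sections 7.2.5 and 8.13 and Table 1 footnote 7 send the assessor to Appendix D or to a standardized protocol. The visit lists in Sections 6.3, 6.4, 6.5.1 and 6.5.2 call for active and passive ROM. None of these places fixes a patient's posture or requires the Baseline posture to be used again.

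External rotation at Week 12 is the fifth and last secondary endpoint in each cohort (Section 7.1.2). It is analysed as change from Baseline and tested in sequence (Section 9.4.1.2). Internal rotation is exploratory (Section 7.1.3).

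**The concern.** A measurement rule for a formally tested endpoint should work in every posture that it permits. Here the permitted sitting posture conflicts with the arm position, the levelling and the vertical reference in the same paragraph. An assessor with a seated patient has no usable written reference for external rotation. The assessor must improvise one, lay the patient down, or record an angle that carries no information on rotation.

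The lack of a same-posture rule adds a second route to error. The endpoint is a within-patient change, so a switch of posture between Day 1 and Week 12 enters the score directly. At stake is the precision of the external rotation comparison, and of the exploratory rotation endpoints, across approximately 35 sites.

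**Working it through.** The plan states no figure on this point, so there is none to reproduce. The check is geometric.

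**Inputs from Appendix D.** Elbow at 90°; abduction a = 0° (adduction) for external rotation and a = 45° or a comfortable angle for internal rotation; stationary arm vertical; patient sitting or supine. **Assumptions.** Sitting means an upright trunk, and abduction is in the frontal plane.

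**Formula.** Let t be true rotation from neutral, with outward rotation positive. The forearm direction is

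cos t × (anterior) + sin t × [cos a × (lateral) + sin a × (cranial)].

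- Supine, vertical is the anterior direction. The cosine of the angle to vertical is cos t, so the reading equals the size of t at any a.
- Sitting, vertical is the cranial direction. The cosine is sin a × sin t, so the acute angle to vertical is arccos(sin a × sin t), using the size of t.

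**Can the start position be reached?** Sitting, the elbow lies below the shoulder by cos a of the humerus length: 100% at a = 0°, 71% at 45°, 0% at 90°. Shoulder and elbow are therefore level only at 90° abduction, which is neither adduction nor 45°. At a = 0° the forearm is horizontal, so it cannot start vertical. Supine, the humerus is level and the neutral forearm is vertical at every a.

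**Readings.** Example for sitting, a = 45°, t = 40°: 0.7071 × 0.6428 = 0.4545, and arccos(0.4545) = 63.0°. The change from neutral is 90.0 − 63.0 = 27.0°.

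| True rotation | Supine | Sitting, external rotation, a = 0° | Sitting, internal rotation, a = 45° | Size of change from neutral, a = 45° |
|---|---|---|---|---|
| 0° | 0° | 90° | 90.0° | 0° |
| 20° | 20° | 90° | 76.0° | 14.0° |
| 40° | 40° | 90° | 63.0° | 27.0° |
| 60° | 60° | 90° | 52.2° | 37.8° |

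Seated external rotation in adduction gives no information on rotation. Seated internal rotation at 45° is offset and compressed but still ordered. At a = 90° the seated angle is 90° − t, so the change equals true rotation and only an offset remains.

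**Direction.** The internal rotation column uses the acute angle. Measured from upward vertical, the same positions read 90°, 104°, 117° and 127.8°. The size of the change is identical and only its sign differs.

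These values follow from applying the seated text literally. They show the fault in the instruction and do not predict trial data.

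**The case against.** **The start position steers the assessor to supine.** The full external rotation set-up can be reached only lying down, and a constant 90° would be obvious. This stands as a reason to expect few literal seated readings. It does not repair a text that expressly permits sitting, and an assessor may instead use an unwritten seated method.

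**Internal rotation may be done at a comfortable angle.** This stands. A reader might infer that all of the rotation text is valid only supine. That is exact for external rotation in adduction and for internal rotation at 45°; seated at about 90° abduction the internal rotation reading is sound apart from an offset. A reader might also infer that a true internal rotation gain from 40° to 60° would appear as a fall of about 10.7° (63.0 − 52.2, before rounding). That sign depends on using the acute angle; from upward vertical it is a rise of the same size. The supportable statement is compression.

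**The design limits the damage.** Treatment is randomized, the assessor is blinded (Section 8.13), and the model adjusts for Baseline score and analysis site (Section 9.4.1.2). The site term can absorb average differences in level from site habits. It cannot remove a change of scale or a posture switch within a patient.

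**Adhesive capsulitis (AC) entry.** A reader might infer that the Screening readings invalidate inclusion criterion 1b. The documents do not support that. Criterion 1b defines its own passive arc, "measured with the patient in supine or sitting position and the shoulder elevated to 45 degrees, compared with the contralateral shoulder", and Section 6.3 requires the site to "Confirm eligibility based on Inclusion and Exclusion Criteria (see Sections 4.1 and 4.2, respectively". An entry measure may differ from an efficacy measure. What remains is a missing detail: Appendix D takes external rotation in adduction, and no Screening item names a reading at 45 degrees.

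**Conclusion.** The point holds for external rotation: a permitted posture makes the written procedure unworkable. It holds in a lesser form for seated internal rotation at 45°, which is compressed. The absence of a same-posture rule holds for all ROM readings, and matters most for rotation because the reference is vertical.

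The expected consequence is non-differential noise or dilution in external rotation at Week 12 and in the exploratory rotation endpoints. Its size cannot be derived, because it depends on the share measured sitting, on what assessors do in that case and on the ROM standard deviation, none of which the documents give.

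A reader might infer bias in favour of one arm or doubt about the main result. Neither follows: nothing ties posture to treatment, the primary and the other four secondary endpoints do not use ROM, and no later test in the sequence depends on external rotation. For AC entry, no changed decision can be shown. The conclusion assumes an upright seated trunk, and that no site manual outside these documents already settles posture.

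**What to change.** In the two rotation paragraphs of Appendix D, specify one patient position that matches the vertical reference (supine does), or give sitting its own valid reference and set-up. Require the same position for each patient from Baseline on, and record it at each ROM assessment. Flag any patients already measured sitting, since two methods would then be mixed in the data.

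As a minor clarification, state which Screening reading supplies the external rotation part of the 45-degree arc in criterion 1b (Synopsis, Populations; Section 4.1).

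The cost is a protocol amendment with IRB approval (Sections 11.9 and 12.1) and an assessor training note.

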### Glenohumeral internal rotation in 45° or comfortable abduction

Internal rotation ROM must be measured with the patient in a sitting or supine position, the shoulder abducted to 45° or comfortable position, and the elbow flexed to 90°. Place a folded towel under the humerus to keep the shoulder and elbow level.

- The patient will be asked to actively internally rotate the shoulder with his/her palm facing medially to end range without scapular compensation. Range of motion will be measured by placing the axis of the goniometer on the olecranon process. The stationary arm will be perpendicular to the floor. The movable arm will be aligned with the ulnar styloid process.
- For passive ROM, the examiner will passively internally rotate the glenohumeral joint until end range is reached, ensuring that there is no scapular compensation.

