#### 7.1.2 Secondary Efficacy Endpoints

The secondary efficacy endpoints comparing FX006 to placebo for each of the shoulder conditions (glenohumeral OA and shoulder AC) in this study include the following:

- Change from Baseline in the weekly mean of the average daily shoulder pain with movement score at Week 12
- Change from Baseline in the SPADI pain subscale at Week 12
- Change from Baseline in the SPADI disability subscale at Week 12
- The PGIC score at Week 12
- Change from Baseline in the ROM of external rotation at Week 12

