#### 7.1.3 Exploratory Efficacy Endpoints

The exploratory efficacy endpoints comparing FX006 to placebo for each of the shoulder conditions (glenohumeral OA and shoulder AC) in this study include the following:

- AUC of change from Baseline in the weekly mean of the average daily shoulder pain with movement score over Weeks 4, 12, 16, 20, and 24
- AUC of change from Baseline in the SPADI pain subscale over Weeks 4, 8, 12, 16, 20, and 24
- AUC of change from Baseline in the SPADI disability subscale over Weeks 4, 8, 12, 16, 20, and 24
- Change from Baseline in the weekly mean of the average daily shoulder pain with movement score at Weeks 1, 4, 8, 16, 20, and 24
- Change from Baseline in the SPADI pain subscale at Weeks 1, 4, 8, 16, 20, and 24
- Change from Baseline in the SPADI disability subscale at Weeks 1, 4, 8, 16, 20, and 24
- Change from Baseline in the SPADI total score at Weeks 1, 4, 8, 12, 16, 20, and 24
- The PGIC score at Weeks 1, 4, 8, 16, 20, and 24
- Change from Baseline in the ROM of external and internal rotation, abduction and flexion at Weeks 4, 8, 16, 20, and 24
- Change from Baseline in the ROM of internal rotation, abduction and flexion at Week 12
- Change from Baseline in the ASES pain subscale at Weeks 1, 4, 8, 12, 16, 20, and 24

- Change from Baseline in the ASES disability subscale at Weeks 1, 4, 8, 12, 16, 20, and 24
- Change from Baseline in the ASES total score at Weeks 1, 4, 8, 12, 16, 20, and 24
- Percent of responders based on the SPADI at Weeks 1, 4, 8, 12, 16, 20, and 24
- Proportion of patients experiencing a  $\geq 20\%$ ,  $\geq 30\%$ , or  $\geq 50\%$  decrease in the weekly mean of the average daily shoulder pain with movement score at Weeks 1, 4, 8, 12, 16, 20, and 24
- Change from Baseline in average weekly rescue medication use
- Change from Baseline in the average weekly SI score
- Change from Baseline in the EQ-5D-5L at Weeks 1, 4, 8, 12, 16, 20, and 24

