### 7.2.5 Active and Passive Ranges of Motion

Active and passive ROM will be assessed with a goniometer per standardized measurement protocol, as outlined in Appendix D at the study visits indicated in Appendix A.

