### **8.13 Index Shoulder Assessment**

The index shoulder assessment will be performed by the blinded assessor at the days indicated in Appendix A. The index shoulder will be assessed for tenderness, heat/redness, swelling, and effusion. The index shoulder assessment will also include a measurement of active and passive ROM. Ranges of motion will be measured with a goniometer and include glenohumeral joint flexion, glenohumeral joint abduction, glenohumeral external rotation, and glenohumeral internal rotation in 45° or comfort abduction as defined in Appendix D. Ranges of motion assessments will be performed bilaterally (on the index and contralateral shoulder) at the Screening Visit.

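### Internal rotation may be read at 45° or at a comfortable abduction angle, with no rule to record or repeat the angle, so its exploratory change-from-Baseline endpoints can mix test position with true motion

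*Combined protocol and SAP*

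**What the plan says.** Appendix D, under internal rotation, gives the test position as "the shoulder abducted to 45° or comfortable position, and the elbow flexed to 90" degrees. The body of the protocol carries the same option: Section 8.13 lists "glenohumeral internal rotation in 45° or comfort abduction as defined in Appendix D". The choice is therefore not a slip confined to the appendix.

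Section 7.2.5 states that "Active and passive ROM will be assessed with a goniometer per standardized measurement protocol", and footnote 7 to Table 1 in Appendix A also calls the method standardized. The detail behind both statements is Appendix D itself.

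Internal rotation enters the analysis only through Section 7.1.3:

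- Week 12: "Change from Baseline in the ROM of internal rotation, abduction and flexion at Week 12".
- Other visits: "Change from Baseline in the ROM of external and internal rotation, abduction and flexion at Weeks 4, 8, 16, 20, and 24".

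The single range-of-motion endpoint above exploratory level is in Section 7.1.2: "Change from Baseline in the ROM of external rotation at Week 12".

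**The concern.** A change from Baseline is interpretable when both readings are taken in the same way. Here the shoulder position may depend on what the patient finds comfortable, and comfort depends on pain and stiffness. A patient who cannot tolerate 45° on Day 1 may be read at a smaller angle, then at 45° once the pain has eased. The difference between the two readings would contain the effect of moving the arm as well as any gain in rotation.

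If this happened equally often in both arms, it would mostly add noise. The trial's hypothesis, however, is that FX006 relieves pain better than placebo (Sections 1.1 and 1.4). If that is so, more FX006 than placebo patients could move from a comfortable angle to 45°, and the position effect would not cancel between arms. Having a blinded assessor does not prevent this, because the patient's own tolerance drives the change.

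At stake is the interpretation of six exploratory comparisons in each cohort.

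**Working it through.** The plan gives no figure for the effect of abduction angle on the reading, so there is nothing to reproduce. The check is of the text, followed by an illustration of size.

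**1. Is the gap closed elsewhere?** The places that could close it are the visit procedures (Sections 6.3, 6.4, 6.5.1 and 6.5.2), Section 7.2.5, Section 8.13, the Schedule of Procedures with its footnotes, and the rest of Appendix D. None says when the comfortable position may replace 45°, asks for the angle to be written down, or requires the Day 1 angle to be used again.

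**2. How are the other rotation measurements treated?**

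| Measurement | Shoulder position | Comfort alternative |
|---|---|---|
| External rotation (Appendix D) | Adduction: "To measure external rotation ROM with the shoulder in the adduction position" | None |
| Rotation arc for AC eligibility (Section 4.1, criterion 1b) | Elevated to 45 degrees | None |
| Internal rotation (Appendix D, Section 8.13) | 45° abduction | Yes |

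The protocol fixes the shoulder position for the other two and leaves it open for internal rotation.

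**3. Would the analysis absorb a shift?** Section 9.4.1.3 has continuous exploratory endpoints analysed similarly to the primary and key secondary ones. The models in Sections 9.4.1.1 and 9.4.1.2 have terms for treatment, Baseline, analysis site, week where relevant and, in AC, pain duration. None has a term for test position.

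**4. How large could it be?** All inputs here are assumptions.

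Spurious between-arm difference = (difference between arms in the share of patients whose angle changes) × (degrees by which that change alone moves the reading).

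- No difference in share: 0 × any shift = 0°.
- Share difference 0.10, shift 5°: 0.10 × 5° = 0.5°.
- Share difference 0.30, shift 15°: 0.30 × 15° = 4.5°.

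A second form splits the shift into a slope (degrees of rotation per degree of abduction, assumed 0.1 to 0.5) and a change of test angle (assumed 10° to 25°):

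- Share difference 0: 0°.
- Share difference 0.10, lower limits: 0.1 × 10° × 0.10 = 0.1°.
- Share difference 0.30, upper limits: 0.5 × 25° × 0.30 = 3.75°.

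The two forms agree on the order of magnitude, and both include zero. These are absolute sizes; the documents do not fix the sign.

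**5. What is not touched?** The primary endpoint is a diary pain AUC. The secondary endpoints are diary pain, two SPADI subscales, PGIC and external rotation. None uses the internal rotation test.

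**The case against.** Four objections have force.

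- **The text permits a shift and does not show one.** The protocol is silent on whether the angle may be chosen afresh at each visit, and a careful site might always use 45°. A reader might infer that the endpoint is biased. The documents support only that it can be.
- **AC may be less exposed.** A reader might infer that stiff, painful AC shoulders would be worst affected. The eligibility criterion points the other way: the rotation arc that qualifies an AC patient is taken at 45° of elevation, so as written eligible AC patients were positioned there around Screening, at most 21 days before Day 1. Sites might apply Appendix D's looser wording at Screening too, so this limits the problem without ruling it out. Patients with glenohumeral osteoarthritis have no such entry measurement, but nothing suggests that 45° is often out of reach for them.
- **A partial check exists.** A reader might infer that the problem could never be examined after the trial. Active and passive abduction are measured by goniometer at the same visits (Section 8.13 and Appendix D), so internal rotation could be re-analysed in patients whose Day 1 abduction was clearly above 45°. Comfort is not the same as end of range, so this is an imperfect proxy. The eCRF is also not among the documents; one can say that the protocol does not require the angle, and no more.
- **The magnitude is assumed.** A 0.30 difference in switching needs at least 30% of FX006 patients to start below 45°, which nothing in the documents supports. They also give no standard deviation or important difference for internal rotation against which to judge 4.5°.

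It may also be said that the sitting-or-supine option ("Internal rotation ROM must be measured with the patient in a sitting or supine position") raises the same kind of issue. It does, and one amendment could cover both, but fixing body position alone would leave the abduction angle open.

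What survives is the gap itself: a written option tied to comfort, with nothing requiring the angle to be recorded or repeated.

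**Conclusion.** The concern holds as a limited measurement weakness. Because the abduction angle may follow comfort and need be neither recorded nor repeated, the exploratory internal rotation changes can mix a change of test position with a true change in motion, possibly at different rates by arm.

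The size is about 0° to 4.5° under assumed inputs: a between-arm difference of 0 to 30 percentage points in the share of patients who change angle, and a shift of 5° to 15° in the reading for each who does. The upper figure multiplies two assumed upper limits and should not be read as an expected value.

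A reader might infer that the trial's range-of-motion evidence as a whole is compromised. The documents do not support that: the secondary range-of-motion endpoint is external rotation, taken in adduction with no comfort alternative. The point is a cheap improvement and does not threaten the trial's main conclusions.

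**What to change.** In Appendix D and Section 8.13:

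- Set each patient's abduction angle on Day 1: 45°, or the largest comfortable angle if 45° cannot be reached. Record it in the eCRF.
- Use that angle for every later index-shoulder internal rotation reading where possible.
- Record the angle actually used at every visit, so that departures are visible.

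In the analysis plan, keep all internal rotation readings in the main analysis and add a sensitivity analysis limited to readings taken at the Day 1 angle. The main analysis should not be restricted in this way: a patient who worsens may be unable to reproduce the Day 1 angle, and setting that visit aside would make missingness depend on outcome.

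The cost is a few sentences of protocol text, one numeric eCRF field completed at each visit, and one additional analysis. No visit, staff or device is added. There are two downsides. Patients who improve are still tested at the smaller Day 1 angle, and the same-angle sensitivity analysis can omit patients who worsen, so it should be read alongside the main analysis.
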